6. COMPLETION OR WITHDRAWAL OF SUBJECTS

6.1. Screen and Baseline Failures

Data for screen and baseline failures will be collected in source documentation at the site but will not be transmitted to the Coordinating Center.

6.2. Subject Completion Criteria

A completed subject is one who has discontinued study treatment for reasons listed in Section 6.3 and completed a post-treatment follow-up visit or has died while receiving study treatment.

6.3. Permanent Discontinuation from Study Treatment

Subjects will receive study treatment until disease progression, death or unacceptable toxicity, including meeting stopping criteria for liver chemistry defined in Section 3.10.1. In addition, study treatment may be permanently discontinued for any of the following reasons:

- deviation(s) from the protocol

CONFIDENTIAL

- request of the subject or proxy (withdrawal of consent by subject or proxy)
- investigator's discretion
- a dose delay of > 21 days unless the investigator or Medical Monitor agree that further treatment may benefit the subject
- intercurrent illness that prevents further administration of study treatment(s)
- subject is lost to follow-up or study is closed or terminated.

The primary reason study treatment was permanently discontinued must be documented in the subject's medical records and electronic case report form (eCRF).

If the subject voluntarily discontinues from treatment due to toxicity, 'adverse event (AE)' will be recorded as the primary reason for permanent discontinuation on the electronic case report form (eCRF).

Once a subject has permanently discontinued from trametinib, the subject will not be re-administered with the discontinued study treatment.

All subjects who discontinue from both study treatments will have safety assessments at the time of discontinuation and during post-study treatment follow-up as specified in Time and Events Table (see Section 7.1).

6.4. Study Completion

Study will be completed having met the study objectives, approximately 24 months after last subject first visit, or when all subjects have withdrawn from the study, whichever occurs first.

6.5. Treatment after the End of the Study

The investigator is responsible for ensuring that consideration has been given for the post-study care of the subject's medical condition whether or not the Coordinating Center is providing specific post-study treatment.

After study participation is completed or terminated, subjects may either:

- Transition to a future rollover study if eligible and continue receiving their current treatment with trametinib

OR

- Complete a follow-up visit within approximately 28 days of the last dose of study treatments if the subject:
 - chooses not to enter the roll-over study, or
 - is withdrawn due to an adverse event (AE) considered related to study treatment, or
 - is considered ineligible to enter the rollover study.

CONFIDENTIAL

7. STUDY ASSESSMENTS AND PROCEDURES

A signed, written informed consent form must be obtained from the subject prior to any study-specific procedures or assessments being performed.

The timing of each assessment is listed in the Time and Events Table (Section 7.1). The timing and number of the planned study assessments may be altered during the course of the study based on newly available data (e.g. to obtain data closer to the time of peak plasma concentrations) to ensure appropriate monitoring for the following assessments: safety, pharmacokinetic (PK), pharmacodynamics (PD)/biomarker or other assessments. The change in timing or addition of time points for any of the planned study assessments listed above must be approved and documented by the Coordinating Center, but this will not constitute a protocol amendment. The institutional review board (IRB) or ethics committee (EC) will be informed of any safety issues that require alteration of the safety monitoring scheme. No more than 100 ml of blood will be collected over the duration of the study, including any extra assessments that may be required.

7.1. Time and Events Table

This section consists of the Time and Events Table (Table 14) and supplemental footnotes to describe assessment windows and sequencing of study-specific assessments and procedures.

Table 14 Time and Events

STUDY PHASES ¹	SCR ²	TREATMENT-One Cycle=28 days			Follow up ³	
		D1	D15 ²¹	Continuation	EOT	Post EOT FU
Visit Window (Days)	-28	N/A	±3	±3	± 3	±7
CLINICAL ASSESSMENTS						
Informed Consent ⁴	X					
Baseline demographics	X					
Medical History	X					
Interim Medical History				Day 1 of each cycle		
Disease Characteristics	X					
Prior Anti-Cancer Therapy	X					
ECOG Performance Status	X	X ⁵		Day 1 of each cycle	X	
SAFETY ASSESSMENTS						
Physical Exam, Weight, Height ¹⁷	X	X ⁵		Day 1 of each cycle	X	
Ophthalmologic Exam ⁶	X (≤35 days)			As clinically warranted	As clinically warranted	
Vital Signs ⁷	X	X	X	Day 1 of each cycle	X	X
12-lead ECG ⁸	X			Cycle 2 day 1, cycle 4 day 1, then every 12 weeks thereafter; more frequently if clinically warranted		X
ECHO or MUGA ⁹	X (≤35 days)			Cycle 2 day 1, cycle 4 day 1, then every 12 weeks thereafter; more frequently if clinically warranted		X ¹⁸
Adverse Events ¹⁰	X			Continuous		X
Concomitant Medications	X			Continuous		X
LABORATORY ASSESSMENTS						
Hematology/Chemistry ²²	X (≤14days)	X ⁵	X	Day 1 of each cycle or more often as clinically warranted	X	X
Coagulation/Urinalysis	X			As clinically warranted		X
Serum Pregnancy Test ¹¹	X (≤14 days)			Cycle 3, day 1, then every 8 weeks		X
Hepatitis B and Hepatitis C ¹⁶	X					
EFFICACY ASSESSMENTS						
Disease assessment/imaging studies	X ¹⁴			Every 8 weeks through week 56 then every 12 weeks thereafter (+/- 7 days)		X ¹⁵

STUDY PHASES ¹	SCR ²	TREATMENT-One Cycle=28 days			Follow up ³	
		D1	D15	Continuation	EOT	Post EOT FU
Visit Window (Days)	-28	N/A	±3	±3	± 3	±7
EXPLORATORY ASSESSMENTS						
Archival tumor tissue ¹⁹	X					
Optional Pre-Dose/Post-Dose Biopsies ¹²	X (≤28 days)		X ²⁰			
Blood Biomarkers	X		X			
Optional Post-Progression Tumor Biopsy ¹³					X	

SCR=Screening, D=Day

- All assessments mandated throughout the study should be performed on the visit day prior to administration of study treatments unless otherwise indicated. Dose modifications of any nature for either study treatment must not alter the pre-planned schedule of visits starting with the first dose of study treatment on Cycle 1, day 1. The start of a Cycle is defined as the day when trametinib administration begins. If a cycle is delayed by one week or less, assessments need not be repeated if results were not clinically significant.
- Assessments within 28 days prior to the first dose of study treatment unless otherwise noted.
- For subjects meeting permanent study treatment withdrawal criteria (Section 6.3), perform follow-up visit approximately 28 days after withdrawal from study treatment. For subjects eligible to continue study treatments in a rollover protocol at study end (Section 6.5), perform follow-up visit just prior to the start of dosing in the rollover trial. Assessments completed at this end of study follow-up visit may be used as baseline values for the rollover trial, provided that these assessments are collected within 14 days of the first dose of study treatment.
- Informed consent may be obtained at any time prior to commencement of screening procedures and does not expire.
- If completed within 72 hrs prior to the first dose of study treatment, this assessment need not be repeated unless clinically indicated. If labs are obtained, inclusion criteria remain the same and subjects may not begin therapy if laboratory parameters have changed outside study limits.
- An ophthalmic examination will be performed as described (see Section 7.3.8).
- Vital signs include temperature, respiratory rate, blood pressure, and pulse rate (see Section 7.3.3).
- For ECG collection, the subject should rest in a semi-recumbent or supine position for at least 5 minutes prior to digital ECG acquisition (see Section 7.3.4).
- LVEF is measured with either ECHO (preferred) or MUGA. The method used to initially document the subject's baseline status must be used consistently throughout the study (see Section 7.3.5).
- From the time of consent until first dose of study treatment: only collect SAEs related to study participation or a Novartis concomitant medication. From Day 1 of study treatment to 28 days after the last dose: collect all AEs and SAEs regardless of causality. From 29 days post treatment and onward, if available: only collect SAEs related to study participation, study treatment, or a Novartis concomitant medication.
- Perform only in women of childbearing potential. Serum testing is required at screening; serum or urine pregnancy test may be used at subsequent time points (see Section 7.3.9).
- If available and with their consent, subjects may choose to provide fresh tumor tissue samples at the times indicated (see Section 0). Samples collected on Day 15 should be collected prior to dosing. Tissue may be obtained through excisional, incisional, core needle, or punch biopsies (or by other methods after discussion with medical monitor.)
- Post-progression tumor tissue collection is optional and should be performed on all consenting subjects within 28 days of disease progression.

14. Baseline CT with contrast (or MRI if CT is contraindicated) should be performed within 28 days of the first dose of study treatment. The method (CT or MRI) used to document the subject's baseline status must be used consistently throughout the study. Subjects with melanoma must also have head MRI to fulfil eligibility criteria. (See Section 7.3.6 details.)
15. Required only if previous assessment was more than 8 weeks prior to follow-up visit.
16. Subjects must be negative for Hepatitis B surface antigen and Hepatitis C antibody at the screening visit. False positive patients may be cleared for enrollment based on RNA-based assays (see Section 7.3.7).
17. Height will be collected at screening only.
18. ECHO/MUGA not required at Follow-up visit if all other on-study LVEF assessments were normal and treating physician feels it is not indicated.
19. Archival tumor tissue (10 unstained slides, 5 micron thickness) will be collected if available for further research if a baseline biopsy is not performed. Efforts should be made to obtain the archival tissue prior to receiving drug; if a plan to receive the tumor tissue is in place, however, day 1 should not be delayed.
20. Optional early on-treatment biopsy may occur on day 15 +/- 3 days.
21. Day 15 visit only for cycle 1; thereafter patients will be seen every 28 days (+/- 3 days).
22. See Table 15 for required laboratory tests.

CONFIDENTIAL

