CONFIDENTIAL

TITLE PAGE

Division: Worldwide Development
Information Type: Clinical Protocol

Title:	[A Phase II Open-Label, Two-Arm Study of the MEK Inhibitor, Trametinib, To Investigate the Safety and Anti-Cancer Activity in Subjects with Melanoma with BRAF non-V600 Mutations]
---------------	--

Compound Number(s): GSK1120212

Vanderbilt-Ingram Cancer Center (VICC) Coordinating Center Protocol Number: VICC MEL 1457

Development Phase: II

Description: This study is a Phase II, open-label, multi-site two-arm study designed to determine the activity and safety of orally administered MEK inhibitor trametinib (GSK1120212), in subjects with melanoma harboring mutations in *BRAF* at locations other than codon 600 (BRAFnonV600^{MUT}) or BRAF fusions. The study will also evaluate the effect of therapy on tumor biomarkers. All patients will receive trametinib 2mg orally administered once daily. Cohort A will consist of subjects with melanoma harbouring mutations which have high or intermediate intrinsic catalytic activity and/or which previously been described sensitive to MEK inhibitors in pre-clinical and/or clinical studies (L597, K601E, G469A, E586K, F595L) as well as BRAF fusions. Cohort B will consist of subjects with melanoma harbouring mutations that have previously been shown to have low affinity for MEK phosphorylation and low intrinsic catalytic activity and/or low sensitivity to MEK inhibitors from previous studies (D594V, G466V, G496R etc), or for which the catalytic activity and effects on sensitization to MEK inhibitors is unknown. The primary endpoint is objective response rate to trametinib for patients in Cohort A; secondary endpoints include objective response rates in Cohort B, safety, progression free survival and overall survival in both treatment arms.

Subject: MEK inhibitor, trametinib, GSK1120212, BRAFV600 wild type, BRAF non-V600 mutant, NRAS wild type, cutaneous melanoma

Author(s): [name]; [name]; [name]; [name]

Copyright Novartis, 2015. All rights reserved. Unauthorized copying or use of this information is prohibited.

CONFIDENTIAL

COORDINATING CENTER / MEDICAL MONITOR INFORMATION PAGE

Medical Monitor and Sponsor Contact Information:

Role	Name	Day Time Phone Number	After-hours Phone/Cell / Pager Number	Fax Number	Address
Primary Medical Monitor	[name]				Vanderbilt-Ingram Cancer Center [name]

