2. OBJECTIVES AND ENDPOINTS

Table 1 lists the objectives and corresponding endpoints.

Table 1 Objectives and Endpoints

	Objectives	Endpoints
Primary	1. To determine the clinical efficacy of trametinib in advanced BRAF nonV600 ^{MUT} melanoma (“high activity” group)	1. Overall response rate (primary statistical endpoint), duration of response, clinical benefit (CR+PR+SD) per RECIST v. 1.1.
Secondary	1. To characterize the safety of trametinib 2. To evaluate the	1. Safety and tolerability as measured by clinical assessments including vital signs and physical examinations, 12-lead

CONFIDENTIAL

[figure not shown]
	time to progression (TTP) and overall survival (OS) of trametinib in advanced BRAF nonV600 ^{MUT} melanoma	electrocardiograms (ECG), echocardiogram (ECHO) or Multi Gated Acquisition (MUGA) scans, chemistry and hematology laboratory values, and adverse events (AEs). 2. TTP and overall survival.
Exploratory	1. To determine the clinical efficacy of trametinib in advanced BRAF nonV600 ^{MUT} melanoma (“low activity/unknown” group) 2. Identify mechanisms of resistance to trametinib in this patient population	1. Overall response rate, duration of response, clinical benefit (CR+PR+SD) per RECIST v. 1.1. 2. Assess molecular characteristics of patient samples, including archival samples, pre-treatment, early while on treatment, and/or at the time of progression

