3.5.4. Rationale for Endpoints

The primary endpoint is to determine the clinical efficacy of trametinib in BRAFnonV600^{MUT} melanoma for Cohort A (“high activity” mutations and BRAF fusions). Response criteria based on RECIST 1.1 will be used to assess complete or partial responses, stable disease, or progressive disease. Safety for both cohorts is a secondary endpoint and as such clinical assessments including vital signs and physical examinations, 12-lead ECG, ECHO, chemistry and hematology laboratory values, retinal exams as needed, and AEs will be monitored and evaluated. Progression free survival and overall survival will be additional secondary endpoints.

The exploratory endpoint is to determine the clinical efficacy of trametinib in Cohort B (“low activity/unknown” group). Response criteria based on RECIST 1.1 will be used to assess complete or partial responses, stable disease, or progressive disease (Eisenhauer 2009). PFS and OS for this cohort will be additional exploratory endpoints.

CONFIDENTIAL

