13.3.2.2.2. Overall Survival and Progression-Free Survival for both cohort A and B

Overall survival, defined as the time from Day 1 of the trametinib therapy to death from any cause. Progression free survival, defined as the time from Day 1 of trametinib therapy to progression of disease as defined by RECIST 1.1 criteria or death, will be reported for each arm. We will also perform subset analysis for PFS stratified by baseline characteristics including LDH level, metastatic stage, and previous therapy (particularly whether a subject has received immune-based therapy).

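### Overall survival is a secondary endpoint, but no vital-status contact is scheduled after one visit about 28 days post-treatment, and no OS censoring rule is stated

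*Combined protocol and SAP*

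**What the plan says.** **The endpoint.** The title-page description lists among the secondary endpoints "safety, progression free survival and overall survival in both treatment arms". Table 1 (section 2) places OS under the secondary objectives. Section 3.5.4 says "Progression free survival and overall survival will be additional secondary endpoints", and its next paragraph calls OS exploratory for cohort B. Section 13.3.2.2.2 covers both cohorts and gives the definition: "Overall survival, defined as the time from Day 1 of the trametinib therapy to death from any cause". No censoring rule follows it.

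**The data collection.** Table 14 has two follow-up columns, end of treatment and one post-treatment visit, and no survival-status row. Its footnote on follow-up tells sites to "perform follow-up visit approximately 28 days after withdrawal from study treatment"; patients moving to a rollover study have the visit just before rollover dosing instead. Section 6.5 describes the same single contact: "Complete a follow-up visit within approximately 28 days of the last dose of study treatments". Section 6.2 then closes the patient's participation: "A completed subject is one who has discontinued study treatment for reasons listed in Section 6.3 and completed a post-treatment follow-up visit".

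**What exists beyond that visit.** Section 8.4 provides a Death eCRF for disease deaths. Table 18 provides a death data collection tool, due within one week of a death being reported. Section 8.5 follows ongoing adverse events to resolution or stabilization. Section 7.5.3.4 asks for effort to document progression after treatment stops. Section 6.4 lets the study run to about 24 months after the last subject's first visit. Sections 13.3 and 13.4 defer analysis detail to the Reporting and Analysis Plan (RAP).

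**The concern.** A site that follows the plan exactly will see each off-treatment patient once more and then has no instruction to find out whether that patient is alive. The death forms record a death once somebody reports it. They do not find deaths, and they do not confirm that the other patients are still living.

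The timing makes this worse than ordinary loss to follow-up. Under section 6.3, "Subjects will receive study treatment until disease progression, death or unacceptable toxicity", so for most patients scheduled contact would end soon after progression, when the risk of death is expected to rise. Censoring then depends on the outcome process itself, and a Kaplan-Meier curve assumes that it does not. A censoring rule in the RAP would define what to do with the dates in hand, but it cannot supply dates that nobody collected. Section 13.3.4 rules out imputation.

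At stake is the OS estimate for two cohorts of at most 25 patients each. OS here is uncontrolled and carries no hypothesis, and the response-rate analysis does not use it.

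**Working it through.** The documents give no OS sample size, event count or follow-up target, so there is no plan figure to reproduce. The calculation below only illustrates size.

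**Inputs from the documents.** Median PFS of 1.7 months (section 1.1), 2.0 and 4.8 months (section 1.2.4). Untreated stage IV median survival of about 6 months, with 26% alive at 1 year (section 1.1). Last contact 28 days (0.92 months) after treatment ends. Study end 24 months after the last first visit (section 6.4).

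**Assumptions.** Exponential times; treatment ends at progression; a share d of PFS events are deaths (0 to 0.2); post-progression median PPS of 1 to 12 months; uniform accrual over 24 months. The exponential form is rough: at a median of 1.7 months it gives 0.5^(6/1.7) = 8.7% progression-free at 6 months, where section 1.1 reports 14.5%.

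**Step 1: share of deaths after the last contact.** This is (1 − d) × exp(−ln 2 × 0.92 / PPS).
- d = 0.2, PPS = 1: 0.8 × 0.529 = 0.42.
- d = 0, PPS = 12: 0.95 (0.94 within the study window).

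**Step 2: anchor PPS to section 1.1.** With a = ln 2/1.7 and b = ln 2/PPS, survival is S(t) = e^(−at) + (1 − d) × a × (e^(−bt) − e^(−at)) / (a − b).
- d = 0, PPS = 3.4: S(6) = 0.087 + 2 × (0.294 − 0.087) = 0.50, matching the 6-month median.
- d = 0, PPS = 4.7: S(12) = 0.0075 + 1.567 × (0.170 − 0.0075) = 0.26, matching 26% at 1 year.
- Allowing d up to 0.2, the two figures give PPS between 3.4 and 5.6 months. These are untreated patients, so the anchor is approximate.

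Over this range, with nothing learned after the visit, 0.8 × exp(−0.638/4.8) = 0.70 up to exp(−0.638/4.7) = 0.87 of deaths are missed.

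**Step 3: error in Kaplan-Meier 6-month OS** (estimate minus truth, percentage points). PFS median is 1.7 months, with 400,000 simulated patients. Patients whose death is not learned of are censored at the visit, or at study end if that is earlier.

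| d, PPS (months) | none learned | 25% | 50% | 75% | all |
|---|---|---|---|---|---|
| 0, 3.4 | +21.5 | +10.6 | +5.4 | +2.1 | −0.1 |
| 0.1, 5.1 | +10.8 | +5.6 | +2.6 | +0.8 | −0.3 |
| 0.2, 5.6 | +4.4 | +2.0 | +0.8 | +0.2 | −0.4 |

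A repeat run with another seed agreed to within 0.2 points. With nothing learned, the OS median is not reached in 33-75% of simulated 25-patient cohorts across the anchored range, against about 0% with full follow-up.

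**Step 4: the wider grid** (PFS 1.7, 2.0, 4.8; PPS 1 to 12; d 0 to 0.2).
- Nothing learned: 42-94% of deaths missed; 1.3-14.4 deaths recorded per 25 patients against 19.5-25.0; 6-month OS off by −3 to +24 points.
- Half learned: −2 to +8 points.
- All late deaths learned but survivors censored at the visit: 12-month OS off by 0 to −6 points, because deaths keep counting while survivors leave the risk set early.
- One cell in full (PFS 4.8, PPS 6, d 0.1, nothing learned): 6-month OS 0.862 against a true 0.777, and 4.7 deaths recorded against 23.3.

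**The case against.** The strongest reply is that the zero-information case is unrealistic. Sites do hear of deaths, and the Death eCRF and the Table 18 tool have somewhere to put them, with no cut-off date. With half of late deaths learned, the anchored error is +1 to +5 points. A 95% interval for a proportion near one half in 25 patients is about ±1.96 × √(0.25/25) = ±20 points. This stands as a limit on the size: the capture rate is unknown, and material bias is possible but not demonstrated.

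Some grid cells also deserve little weight. The −3 points comes from PFS 1.7, PPS 12, d 0.2, where the monthly hazard of death before progression (0.2 × ln 2/1.7 = 0.082) exceeds that after it (ln 2/12 = 0.058). The anchored figures are the ones to use.

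The 24-month window in section 6.4, and section 13.4's inclusion of all data to study completion or withdrawal regardless of treatment duration, suggest that longer follow-up was intended. That is plausible, but neither sets a contact, and section 6.2 pulls the other way. The Table 14 footnote limiting collection from day 29 to related SAEs governs adverse events; it does not forbid survival data, but nothing else asks for them.

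The study schematic is not visible and might show a follow-up phase. However, section 7 makes Table 14 the schedule, and its footnote, 6.2 and 6.5 agree on one post-treatment visit. The RAP may state a censoring rule, so that half of the point is partly a request to confirm.

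**Conclusion.** The point holds and should be fixed. OS is promised for both cohorts, and the plan schedules no means of knowing who has died or is alive beyond about four weeks after treatment. Loss of vital status is thereby tied to progression, which no later analysis rule can repair.

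The direction depends on how many late deaths surface informally. With none, OS is mostly overstated: +4 to +22 points at 6 months under the section 1.1 anchor. With all late deaths recorded and survivors censored at the visit, it is slightly understated: about 0 to −1 point at 12 months under the same anchor. These sizes rest on exponential times, treatment ending at progression, and post-progression survival inferred from untreated patients. The absence of scheduled contact rests on the text alone.

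**What to change.** - Add a survival-status row to Table 14: a phone or chart check at a fixed interval from the post-treatment visit until death or study end, recording date of death or date last known alive. Every 12 weeks would match the late imaging interval already in that table.
- State in 13.3.2.2.2, or confirm in the RAP, that OS is censored at the date last known alive.
- State in 6.2 that the 28-day visit does not end survival follow-up, and bring 6.4 and 14.6 into line.
- If survival contact is not wanted, remove OS as an endpoint.

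Table 1 names TTP where 3.5.4 and 13.3.2.2.2 name PFS; that is a separate point to reconcile.

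**Cost.** A protocol amendment and possibly consent wording for later contact. Section 7 lets the Coordinating Center change the timing of planned assessments, or add time points, without an amendment, but vital status is not among the assessments in Table 14, so relying on that is doubtful. For at most 50 patients, 12-weekly checks come to about 95-130 in total under the section 1.1 anchor, and about 270 (5.4 per patient) at a post-progression median of 12 months. With 24-month accrual, the earliest enrollees could be followed for up to about 48 months. No visits or procedures are added, and the sample size and primary analysis do not change.
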